# C. ADDITIONAL PRINCIPLES FOR MEDICAL RESEARCH COMBINED WITH MEDICAL CARE

- 28. The physician may combine medical research with medical care, only to the extent that the research is justified by its potential prophylactic, diagnostic or therapeutic value. When medical research is combined with medical care, additional standards apply to protect the patients who are research subjects.
- 29. The benefits, risks, burdens and effectiveness of a new method should be tested against those of the best current prophylactic, diagnostic, and therapeutic methods. This does not exclude the use of placebo, or no treatment, in studies where no proven prophylactic, diagnostic or therapeutic method exists.
- 30. At the conclusion of the study, every patient entered into the study should be assured of access to the best proven prophylactic, diagnostic and therapeutic methods identified by the study.
- 31. The physician should fully inform the patient which aspects of the care are related to the research. The refusal of a patient to participate in a study must never interfere with the patient-physician relationship.
- 32. In the treatment of a patient, where proven prophylactic, diagnostic and therapeutic methods do not

exist or have been ineffective, the physician, with informed consent from the patient, must be free to use unproven or new prophylactic, diagnostic and therapeutic measures, if in the physician's judgment it offers hope of saving life, re-establishing health or alleviating suffering. Where possible, these measures should be made the object of research, designed to evaluate their safety and efficacy. In all cases, new information should be recorded and, where appropriate, published. The other relevant guidelines of this Declaration should be followed.

# APPENDIX C: GLABELLAR LINE SCALE (GLS) AT MAXIMUM FROWN

# **APPENDIX D: GLOBAL AESTHETIC IMPROVEMENT SCALE (GAIS)**

GAIS Grade	Score	Description
Much Improved	2	Marked improvement in appearance
Improved	1	Improved in appearance, but would like more
No Change	0	The appearance is essentially the same as the original condition
Worse	-1	The appearance is worse than the original condition
Much Worse	-2	The appearance is much worse that the original condition

# **APPENDIX E: SUBJECT SATISFACTION SCALE (SSS)**

SSS Grade	Score	Description
Very Satisfied	2	I am very satisfied with the treatment
Satisfied	1	I am satisfied with the treatment
Indifferent	0	I am indifferent with the treatment
Unsatisfied	-1	I am unsatisfied with the treatment
Very Unsatisfied	-2	I am very unsatisfied with the treatment

7.5.2. Per-Protocol Population	
7.5.3. Safety Population	
7.6. Sample Size Considerations	
7.7. General Considerations	
APPENDIX A: STATISTICAL TABLES	

Version 1.1 31-May-2023 Confidential Page 6/58

ABBREVIATIONS

ADDREVIATI	
AE	Adverse Event
BLA	Biologic License Application
BP	Blood Pressure
CFR	U. S. Code of Federal Regulations
CI	Confidence Interval
CRA	Clinical Research Associate
CRO	Clinical Research Organization
ECG	Electrocardiogram
ET	Early Termination
eCRF	electronic Case Report Form
FDA	Food and Drug Administration
GCP	Good Clinical Practices
GAIS	Global Aesthetic Improvement Scale
GLS	Glabellar Line Scale (0=none, 1=mild, 2=moderate, 3=severe)
HIPAA	Health Insurance Portability and Accountability Act
ICF	Informed Consent Form
ICH	International Conference on Harmonization
IND	Investigational New Drug
IP	Investigational Product
IRB	Institutional Review Board
ITT	Intent-to-Treat
PI	Principal Investigator
PP	Per protocol
SAE	Serious Adverse Event
SAFT	Safety
SAP	Statistical Analysis Plan
SMMP	Safety and Medical Monitoring Plan
SOC	System Organ Class
SSS	Subject Satisfaction Scale
TRAE	Treatment Related Adverse Event
UADR	Unanticipated Adverse Drug Reaction
ULN	Upper Limit of Normal
UPT	Urine Pregnancy Test
US	United States

Confidential Page 7/58

evolus™

This Statistical Analysis Plan (SAP) gives a comprehensive and detailed description of statistical techniques to be used for study EVOLUS-CLIN201. The purpose of this SAP is to ensure the credibility of the study findings by pre-specifying the statistical approaches for the analysis of study data prior to database lock. This SAP provides additional details concerning the statistical analyses outlined in the protocol. Whenever differences exist in descriptions or explanations provided in the protocol and SAP, the SAP prevails.

1.1. Background

Botulinum toxin type A, now manufactured by several pharmaceutical/biotechnology companies, has been approved for the temporary improvement in the appearance of moderate to severe glabellar lines associated with corrugator and/or procerus muscle activity in adult subjects.

The clinical study designs that have supported the New Drug Applications for these products have generally followed the same pattern in that they were all multicenter, randomized, double-blind, placebo-controlled studies that assessed the efficacy of the product to reduce the severity of glabellar lines at 30 days following injection of the targeted glabellar muscles.

More recently, botulinum toxins approved in the US have investigated the effect of increasing dose on duration of effect. In this clinical investigation, the dose of prabotulinumtoxinA will be increased and the safety and duration of effect will be studied.

1.2. Rationale for Study

PrabotulinumtoxinA, using a total dose of 20 Units (i.e., 4 Units injected into five sites of the glabellar complex muscles), has been approved by the FDA for the treatment of moderate to severe glabellar lines. The current study will explore the safety and effectiveness of injecting 40 Units of prabotulinumtoxinA into the glabella and determine if the duration of effect of prabotulinumtoxinA 40 Units is superior to that of prabotulinumtoxinA 20 Units.

Exploratory analyses will determine if the duration of effect of prabotulinumtoxinA 40 Units is superior to that of onabotulinumtoxinA 20 Units, as well as if the duration of effect of prabotulinumtoxinA 20 Units is superior to that of onabotulinumtoxinA 20 Units.

1.3. Statistical Hypothesis

The general form of duration of effect hypotheses will be:

H_o: β = 0H_A: β < 0

where $\exp(\beta)$ is the hazard ratio (experimental treatment / comparator treatment) for loss of effect. The study is not powered for formal hypothesis testing and any analyses presented will be for interpretation purposes only.

1.4. Study Objectives

The primary objectives of this study are to demonstrate the safety and duration of effect of 40U of prabotulinumtoxinA-xvfs in providing temporary improvement in the appearance of moderate to severe glabellar lines associated with corrugators and/or procerus muscle activity in adult subjects.

Confidential Page 8/58

2. OVERVIEW OF STUDY DESIGN

2.1. Study Design

This is a multicenter, prospective, randomized, double-blind, active-controlled, single-treatment, increasing dose design.

Approximately 150 subjects will be randomized 1:1:1, to either 20U onabotulinumtoxinA, 20U prabotulinumtoxinA-xvfs, or 40U prabotulinumtoxinA-xvfs. Subjects with moderate or severe glabellar lines at maximum frown on the 4-point validated Glabellar Line Scale (*GLS*, 0=none, 1= mild, 2=moderate, 3=severe), as judged by the investigator and the subject, will be eligible.

Safety and effectiveness will be assessed on days 3, 7, and 30, then every 30 days up to 365 days or until the subject has returned to Baseline as assessed by the Investigator, at which point the subject will exit the study. Please refer to Table 1 below for visit specifics.

Duration of effect will be estimated by Kaplan-Meier analysis and will be based on the number of days from Treatment Day (Baseline) to the day that GLS severity (Investigator assessment) at maximum frown returns to the Baseline value (i.e., the treatment will be considered to remain effective for the amount of time during which GLS severity at maximum frown has not returned to Baseline severity).

The Evaluating Investigator (i.e., Blinded Investigator) will be responsible for managing the subject, monitor for related and unrelated adverse effects, and carrying out the evaluations. Injections of study drug will be performed by an "Unblinded Injector" (i.e., physician or nurse practitioner not responsible for subject follow-up).

2.2. Study Population

The full list of inclusion and exclusion criteria can be found in the Study Protocol.

2.3. Primary Endpoint

The primary effectiveness endpoint will be duration of effect, defined as the number of days from Treatment Day (Baseline) to the day that GLS severity (Investigator assessment) at maximum frown returns to the Baseline value. The treatment will be considered to remain effective for the amount of time during which GLS severity at maximum frown has not returned to Baseline severity. Duration of effect will be estimated by Kaplan–Meier analysis.

Although the trial is not powered for inferential analysis, this will be the most influential outcome in the overall assessment of the effectiveness of prabotulinumtoxinA 40 Units, compared to prabotulinumtoxinA 20 Units, in treating moderate to severe glabellar lines.

Confidential Page 9/58

TABLE 1. SCHEDULE OF EVENTS AND PROCEDURES

Visit Number	V1 ¹ Screening	V2 ¹	V3	V4 (phone f/u)	V5 to V15 ²	V16 ³ (or Final Visit, or ET)	Unscheduled Visit 11
Day/Week/Month	≤ 14D	Tx Day	48Hr	D 7	D30 to D330 Monthly Visits	D365	
Visit Windows				±1 Day	D30 ±3D, ≥D60 ±7D	±14D	
Assessment and Procedures							
Informed Consent	X						
Inc/Excl Criteria	X						
Demographics, Med Hx	X						
Randomization to Study Tx 4		X					
Effectiveness - Investigator							
Glabellar Line Scale ⁵	X	X	X		X	X	X
Global Aesthetic Improvement			X		X	X	X
Effectiveness - Subject							
Glabellar Line Scale ⁵	X	X	X		X	X	X
7-Day Subject Diary		Х —		—			
Global Aesthetic Improvement			X		X	X	X
Subject Satisfaction Score			X		X	X	X
Clinical Interview 6					D30 only	X	X
Safety Evaluations							
Directed Questionnaire ⁷	X		X		X	X	X
Directed Review of Systems	X		X		X	X	X
Vital Signs 8	X		X		X	X	X
Physical Exam 9	X		X		X	X	X
UPT (as applicable)	X	X				X	
Clinical Laboratory Tests 10	X					X	X
ECG	X					X	X
Safety Assessment Phone Call				X			
Brow Area Photography	X	X	X		X	X	X
Concomitant Medications	X	X	X	X	X	X	X
AE Assessment		X	X	X	X	X	X

- 1. Screening and treatment visit can take place the same day, at the discretion of the investigator
- 2. Subjects will be followed monthly until their Glabellar Line Scale score is back to Baseline (Investigator assessment)
- 3. Subject exits study once their Glabellar Line Scale Score has returned to Baseline (Investigator assessment)
- 4. IP may be administered same day as Screening
- 5. Glabellar Line Scale at Maximum Frown, 0=none, 1=mild, 2=moderate, 3=severe
- 6. Clinical Interview Questions
 - What did you like about the treatment (clinically or other feedback)?
 - What did you dislike about the treatment (clinically or other feedback)?
 - If treated with botulinum toxin before this study, which treatment did you prefer, the study treatment or the previous treatment?
- 7. Directed Questionnaire: Have you noticed any problems with speaking, swallowing, or breathing? Have you had any headaches, eyelid or eyebrow drooping?
- 8. Blood pressure, heart rate, respiration rate
- 9. Physical exam to be based on the Investigator judgment as a response to the Medical History, Questionnaire, Review of Systems, and any other relevant information. Neurological exam includes extraocular movement, cranial nerve and muscle weakness assessment
- 10. Clinical Laboratory Tests:
 - Hematology: Hemoglobin, Hematocrit, RBC, WBC, WBC differential, Platelets
 - Serum: ALP, BUN, Creatinine, ALT, AST, Alb, total protein, UA, Glucose, Na, K, Cl, Ca, anti-botulinum toxin antibodies
 - Urinalysis: Specific Gravity, pH, Protein, Glucose, WBC, Blood
- 11. Unscheduled Visit: May occur at any time during the study to complete missed study procedures, assess AEs, or assess ongoing unresolved drug-related AEs after study exit. During a visit, some or all of the safety and effectiveness evaluations may be performed.

Version 1.1 31-May-2023 Confidential Page 10/58

3. SUBJECT NUMBERING, RANDOMIZATION AND BLINDING

3.1. Subject Numbering

All subjects will receive a 3-digit subject number, starting at 001. Subject numbers will be assigned at site level and in ascending order and will be coupled with the site identification number for unique identification of each subject. Subjects withdrawn from the study will retain their subject number; new subjects will be allocated a new subject number.

Subjects who do not meet eligibility criteria will be deemed screen failures. Screen Failures will not be entered in the eCRF. However, these subjects may be re-screened at a later date.

3.2. Subject Randomization

At Visit 2/Treatment Day, subjects will be randomized (1:1:1 ratio) to treatment with either 20U onabotulinumtoxinA, 20U prabotulinumtoxinA-xvfs, or 40U prabotulinumtoxinA-xvfs.

Subjects will be randomized using a blocked randomization scheme that will be stratified by the following factors:

• Baseline GLS: moderate vs. severe

• Age group: <65 vs. >65 within each stratum

• Gender: female vs male

3.3. Blinding

To maintain study blind, the "Unblinded Injector" (i.e., physician or nurse practitioner not responsible for subject follow-up) will have access to the Randomization Schedule, be aware of treatment assignment, will prepare syringes of reconstituted IP, and will administer injections of study drug to study subjects.

3.4. Unblinding

The study blind will be broken only after all data are verified, entered into the database and validated, and the database is locked.

Version 1.1 31-May-2023 Confidential Page 11/58

4. STUDY TREATMENT

Subjects will be treated either with the study drug 40U of prabotulinumtoxinA or one of the two controls; 20U of prabotulinumtoxinA or 20U of onabotulinumtoxinA.

The reconstitution and syringe preparations will be done in a double-blinded fashion.

4.1. Concomitant Medications

All treatment/procedures received by the subject within 14 days prior to Visit 2 (Treatment Day) and throughout the treatment period, including the name of the treatment/procedure, must be recorded in the eCRF with start date, stop date, dosage, frequency and indication, if applicable.

EVOLUS-CLI	N2	201
Statistical Analys	sis	Plan

Confidential Page 12/58

5. STUDY EVALUATIONS

5.1. Effectiveness Assessments

5.1.1. Glabellar Lines Scale (GLS)

The severity of glabellar lines at "maximum frown" will be assessed by both the Investigator (Blinded Evaluator) and subjects using the validated 4-point GLS as per Table 2.

Table 2. GLS at Maximum Frown

Grade	Score	Description
None	0	No lines
Mild	1	Line seen, not sharp
Moderate	2	Line sharper, deep, may see heaping of skin
Severe	3	Deeper line, heaping of skin, skin may be opposed

5.1.2. Global Aesthetic Improvement Scale (GAIS)

GAIS will be assessed by both the Investigator (Blinded Evaluator) and subjects using the 5-grade scale as per Table 3.

Table 3. GAIS

Grade	Score	Description
Much Improved	2	Marked improvement in appearance
Improved	1	Improved in appearance, but would like more
No Change	0	The appearance is essentially the same as the original condition
Worse	-1	The appearance is worse than the original condition
Much Worse	-2	The appearance is much worse that the original condition

5.1.3. Subject Satisfaction Scale (SSS)

SSS will be assessed by the subject using the following 5-grade scale as detailed in Table 4.

Table 4. Subject Satisfaction Scale

Grade	Score	Description
Very Satisfied	2	I am very satisfied with the treatment
Satisfied	1	I am satisfied with the treatment
Indifferent	0	I am indifferent with the treatment
Unsatisfied	-1	I am unsatisfied with the treatment
Very Unsatisfied	-2	I am very unsatisfied with the treatment

Clinical Interview (Day 30, Final Visit/Early Termination, and Unscheduled Visit)

5.1.4. Clinical Interview (Day 30, Final Visit/Early Termination, and Unscheduled Visit)

Subject opinion regarding study treatment will be assessed through a clinical interview employing the following questions:

- What did you like about the treatment (clinically or other feedback)?
- What did you dislike about the treatment (clinically or other feedback)?
- If treated with botulinum toxin before this study, which treatment did you prefer, the study treatment or the previous treatment?

Version 1.1 31-May-2023 Confidential Page 13/58

5.1.5. 7-Day Subject Diary

In the morning of the day after study treatment, subjects will be issued a 7-day electronic subject diary that will assess subjects' opinion regarding onset of study treatment effect. Subjects will respond "Yes" or "No" to the following question: "Since being injected, have you noticed any effect on the appearance of your glabellar lines?"

Version 1.1 31-May-2023 Confidential Page 14/58

6. SAFETY ASSESSMENTS

6.1. Directed Questionnaire

The following questions will be asked looking for signs of local or distant botulinum toxin spread and to set a baseline:

- Have you noticed any problems with speaking, swallowing, or breathing?
- Have you had any headaches, eyelid or eyebrow drooping?

6.2. Directed Review of Systems

Directed Review of Systems will include review of the following systems: Head and Neck, Respiratory, Cardiovascular, Neurological, Musculoskeletal, Dermatological.

6.3. Vital Signs

Blood pressure (systolic, diastolic), respiratory rate, and heart rate will be recorded.

6.4. Physical Exam

Based on the response to the medical history, directed questions, directed reviews of systems, inclusion and exclusion criteria, an appropriate physical examination will be conducted by the Investigator. The neurological examination should include extraocular movement, cranial nerve and muscular weakness assessments. This exam will also establish a baseline for the subject.

6.5. Urine Pregnancy Test

UPTs will be conducted at Screening (Visit 1), Visit 2 (if applicable) and end of study. Pregnancies will be recorded using the Unanticipated Problems Reporting Form and are not be considered AEs.

6.6. Clinical Safety Laboratory Tests

The clinical laboratory data consist of blood analysis (including hematology, clinical chemistry, and urinalysis) will be conducted as per the visit schedule. Clinically significant results (Investigator opinion) will be reported as AEs.

The following tests will be performed:

- Hematology: hemoglobin, hematocrit, red blood cell count, white blood cell count, neutrophils, lymphocytes, monocytes, eosinophils, basophils, platelet count
- Chemistry: alkaline phosphate, urea nitrogen, creatinine, ALT, AST, albumin, total protein, uric acid, glucose, sodium, potassium, chloride, calcium
- Urinalysis: specific gravity, pH, protein, glucose, leukocytes, occult blood
- Botulinum antibodies

6.7. 12-Lead ECG

12-lead ECGs will be at Screening and at the final study visit and will include heart rate, PR, QRS, QT, and QTc. ECG results will be interpreted by as Normal, Abnormal; not clinically significant (NCS), or Abnormal; clinically significant (CS). If Abnormal, details will be provided, and "Abnormal Clinically Significant" results (Investigator opinion) will be reported as AEs."

6.8. Concomitant Medications

All treatment/procedures received by the subject within 14 days prior to study treatment and

Version 1.1 31-May-2023 Confidential Page 15/58

throughout the treatment period, including the name of the treatment/procedure, must be recorded in the eCRF with end dates, if applicable.

6.9. Adverse Events

The Blinded Investigator will assess for all types of AEs and will record details of seriousness, severity, duration, and action taken with the study IP, and relationship to the IP. AEs will be reported from the time of consent until the final visit.

Treatment-Related AEs will be followed until the event has resolved or stabilized or until follow-up is no longer possible or the PI deems it unnecessary.

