#### 10.5.6.1 All Adverse Events

All AEs, whether serious or not, will be recorded from the time of IP injection until the last study visit. A blinded Investigator will assess all AEs and record details of seriousness, severity, date of onset, date of resolution or stop date, and action taken with study treatment, and relationship to the IP.

If an AE occurs, the first concern will be the safety of the study subjects. All Treatment-Related AEs will be followed until the event has resolved or stabilized or until follow-up is no longer possible or the blinded Investigator deems it unnecessary.

If the Sponsor determines that an AE presents an unreasonable risk to subjects, the Sponsor will terminate participation in the study as soon as possible (i.e., within 5 working days after the Study Sponsor makes this determination and not later than 15 days after the Study Sponsor first receives notice of the event).

The Sponsor is responsible for ensuring that reporting of AEs to the relevant governing authorities is within the time frame applicable according to international and local law.

In the event that adjudication of a safety issue is required, an independent committee will be convened. The committee will be comprised of three medical doctors, one dermatologist, and two plastic surgeons.

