#### 10.5.6.2 Serious Adverse Events (SAEs)

All SAEs that occur after the time of IP injection through 7 days after subject completion of the study must be reported to ethica CRO within 24 hours of awareness. Initial report must be made by completing the paper SAE Report Form with all available information and providing it to ethica CRO by email. It is the site's responsibility to perform the following:

- Obtain and maintain all pertinent medical records, information, and medical judgments from colleagues who assisted in the treatment and follow-up of the subject.
- Provide ethica CRO with a complete, written case history, including copies of pseudonymized supporting reports (e.g., progress notes, laboratory reports) and a statement as to whether the event was or was not related to study treatment.
- With the assistance of the CRO, notify the governing IRB of the SAE in accordance with the requirements of SAE reporting stipulated by the governing IRB.

Serious Adverse Event Reporting: The PI will report SAEs by email using the paper SAE report form within 24 hours of awareness and complete the eCRF within 48 hours of awareness. SAE reports should be scanned and emailed to the ethica CRO Clinical Project Manager. ethica CRO will handle the SAE report according to the process described in the SMMP. Any missing or additional relevant follow-up information concerning the SAE should be sent to ethica CRO as soon as possible, together with the following information, at a minimum: initial report, AE, date of occurrence, subject identification, study ID, and site number; this will allow the follow-up information to be linked to the initial SAE report. Specific information may be requested by opening queries in the eCRF or via e-mail communication.

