6.9.2. Severity Assessment

For all types of AEs, the Blinded Investigator will determine the severity classification based on his/her clinical experience and by using the following definitions of severity:

- **Mild:** Symptoms are barely noticeable or do not make the subject uncomfortable. The AE does not influence performance or functioning. Prescription drugs are not ordinarily needed for relief of symptom(s).
- **Moderate:** Symptoms are of sufficient severity to make the subject uncomfortable. Performance of daily activities is influenced. Treatment of symptom(s) with prescription drugs or therapies may be needed.
- **Severe:** Symptoms are of sufficient severity to cause the subject severe discomfort. Performance of daily activities is compromised. Treatment for symptom(s) with prescription drugs or therapies may be needed.

Version 1.1 31-May-2023 Confidential Page 16/58

The maximal severity for the AE will be recorded, even if the AE presented as being less severe at some point during the event.

Adverse Events of Special Interest (AESI) Reporting

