7.4.1. Adverse Events (AEs)

AEs will be coded to system organ class (SOC) and preferred term (PT) using the Medical Dictionary for Regulatory Activities (MedDRA). The number and percentage (incidence) of subjects reporting an AE and the number of AEs will be summarized. A treatment-emergent AE will be defined as AEs that started at or after the first injection.

The following AE incidence tables will be provided for treatment-emergent AEs:

- AE Profile Overview
- Treatment-Emergent AEs by SOC and PT
- Treatment-Related AEs by SOC and PT
- Treatment-Emergent SAEs by SOC and PT
- Treatment-Related SAEs by SOC and PT
- Unexpected Adverse Drug Reactions by SOC and PT
- Adverse Events of Special Interest by SOC and PT

Treatment-related AEs will be defined as possibly, probably, or definitely related. Two-sided Wilson 95% confidence intervals will be calculated for the overall incidence of AEs and SAEs.

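### The SAP starts adverse event reporting at consent, the protocol at injection; with a treatment-emergent rule based on start date alone, a screening-onset event that worsens after injection may reach no AE table, and the tabulation of SAEs after exit is left unclear

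*SAP*

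**What the plan says.** **Start of the window.** SAP 6.9 says that "AEs will be reported from the time of consent until the final visit". Protocol 10.5.6.1 says: "All AEs, whether serious or not, will be recorded from the time of IP injection until the last study visit". In Table 1 of both documents the AE assessment row is first marked at Visit 2, the Treatment Day, with nothing at screening. Protocol 10.2.1 allows treatment on the day of screening or within 14 days of it.

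**End of the window.** SAP 6.9 and Protocol 10.5.6.1 both stop at the last visit. For serious events, Protocol 10.5.6.2 goes further: "All SAEs that occur after the time of IP injection through 7 days after subject completion of the study must be reported".

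**Which document rules.** The SAP introduction says: "Whenever differences exist in descriptions or explanations provided in the protocol and SAP, the SAP prevails".

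**What is counted.** SAP 7.4.1 says: "A treatment-emergent AE will be defined as AEs that started at or after the first injection". Protocol 12.5.1 has the same sentence. SAP 7.4.1 then lists seven AE incidence tables, all for treatment-emergent AEs. On severity, SAP 6.9.2 (and likewise Protocol 10.5.5) says: "The maximal severity for the AE will be recorded, even if the AE presented as being less severe at some point during the event".

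**Worsening.** Protocol 10.5 has subjects asked about new or worsening symptoms at each visit. Protocol 10.5.1 does not count recurring symptoms of a pre-existing condition as AEs unless their severity or frequency rises to a clinically significant degree.

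**The concern.** Safety of the 40-unit dose is a primary objective, and worsening of a recent complaint such as headache is one way a higher dose could show harm. If the database holds a record that opened in screening, the start-date rule classes it as not treatment-emergent whatever happens after injection. The post-injection change then leaves no trace in the AE tables. The same subject could be counted under one document and not under the other, and the SAP gives itself precedence.

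For serious events the risk is a mismatch between outputs. Sites must report SAEs for a week after completion, but the SAP's collection sentence ends before that week and nothing says whether those SAEs enter the tables. Safety reports and study tables could then differ with no stated reason.

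**Working it through.** The plan gives no figure on this point, so there is nothing to reproduce. The check is a comparison of the texts, followed by a rough count.

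**Step 1. Windows side by side.**

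| Source | Start | End |
|---|---|---|
| Protocol 10.5.6.1 (all AEs, serious or not) | injection | last study visit |
| Protocol 10.5.6.2 (SAEs) | injection | 7 days after completion |
| Table 1, both documents | Visit 2, Treatment Day | final or early termination visit |
| SAP 6.9 | consent | final visit |

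SAP 6.9 is the only source that starts at consent. Its window includes serious events, because the same paragraph says that "The Blinded Investigator will assess for all types of AEs and will record details of seriousness". At the end, SAP 6.9 agrees with Protocol 10.5.6.1. The outlier is Protocol 10.5.6.2, so the disagreement about SAEs also lies inside the protocol.

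**Step 2. An event that starts in screening and worsens.** Suppose a headache begins after consent and before injection, and becomes clearly worse after injection.
- Under SAP 6.9 it is an AE from its onset. If it stays one record (SAP 6.9.2), that record carries the higher severity and the pre-injection start date. It fails the rule in SAP 7.4.1 and so enters none of the seven tables.
- Under the protocol, AE recording has not opened at onset. A clinically significant worsening can be recorded as an AE after injection (10.5.1) and would then be tabulated.
- Neither document says what start date a worsening carries, so the result depends on how the site enters it.

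**Step 3. An SAE in the 7 days after completion.** The investigator must send the form to the CRO "within 24 hours of awareness and complete the eCRF within 48 hours of awareness". The event started after injection and the treatment-emergent rule has no upper time limit, so it qualifies. It would be left out only if the sentence in SAP 6.9 were applied as an analysis cut-off, which the SAP neither states nor rules out.

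**Step 4. Size of the screening gap.** Inputs from Protocol 1.1: placebo AE incidence p of 26.9% (EV-002), 32.1% (EV-001) and 32.7% (EVB-003), each over 150 days. With a constant rate, expected subjects with an onset in d days = 150 × [1 − (1 − p)^(d/150)].
- d = 14: 4.3, 5.3 and 5.4 subjects.
- d = 1: 0.3, 0.4 and 0.4 subjects.
- Headache alone (placebo 7.6%), d = 14: 150 × [1 − 0.924^(14/150)] = 1.1 subjects.

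The documents do not say what share would worsen. Assuming 10% to 50%, the 14-day case gives 4.3 × 0.10 = 0.4 to 5.4 × 0.50 = 2.7 subjects over all three arms. With 50 per arm, one subject is 1/50 = 2 percentage points of an arm's incidence.

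**Step 5. Size of the post-exit window.** Expected subjects with an SAE = (x/n) × (7/T) × 150, with x, n and follow-up T from Protocol 1.1.
- EV-002: 4/246 × 7/150 × 150 = 0.11.
- EV-001 (3/246) and EVB-003 (3/245), T = 150: 0.09 each.
- EV-004: 7/352 × 7/365 × 150 = 0.06.
- EV-006: 7/570 × 7/365 × 150 = 0.04.

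The chance of at least one, 1 − exp(−expected), runs from 3.5% to 11%.

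**The case against.** The strongest reply is that sites work to the protocol. They open AE recording at injection, and neither schedule has an AE assessment at screening, so there may be no pre-injection record to absorb a later worsening. Protocol 10.5.1 already covers complaints that predate enrolment. The loss in Step 2 needs a site to record an AE in screening and then to fold the worsening into it. Much of this stands: it limits the problem to onsets between consent and injection and makes it conditional on how the worsening is recorded. It does not remove the contradiction, since the SAP prevails by its own words and no text settles the recording.

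Second, other planned outputs show status after injection. The directed questionnaire is tabulated by visit, and the review of systems and physical examination have shift tables. A reader might infer that such a worsening vanishes from the safety results altogether. The documents do not support that; the gap is in the AE tables. The questionnaire is yes/no, however, so a headache present at baseline that worsens stays a yes.

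Third, a reader might infer that the SAP contradicts the protocol at both ends of the window. It does not. For non-serious AEs the ends agree, and for SAEs the protocol disagrees with itself. The treatment-emergent sentence is also the same in both documents, so the missing worsening clause is a shared gap and not an SAP departure.

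Fourth, the expected counts are close to zero. That is correct, and it bears on priority.

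**Conclusion.** The contradiction at the start of the window is plain text: SAP 6.9 differs from Protocol 10.5.6.1, Protocol 10.5.6.2 and the SAP's own Table 1. Its consequence, a screening-onset event that worsens and reaches no AE table, follows from the stated rules provided the event is kept as one record.

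The stronger reading that SAEs in the week after exit are excluded does not hold. They meet the treatment-emergent rule and reach the eCRF; their tabulation is ambiguous.

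The effect is very small. The 4.3 to 5.4 subjects assume that all 150 use the full 14 days and have AEs at a constant placebo rate, and they count any onset, not worsening. Treatment on the day of screening takes the number towards zero. The 0.04 to 0.11 subjects with an SAE after exit assume that rates from the previous trials carry over unchanged. The change is still worth making before database lock: it removes a possible undercount on a primary objective, and in arms of 50 a single subject is visible.

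**What to change.** 1. Reconcile the start of AE collection across Protocol 10.5.6.1 and 10.5.6.2, SAP 6.9 and the SAP's Table 1.
2. In SAP 7.4.1 and Protocol 12.5.1, define a treatment-emergent AE as one that started, or worsened in severity or frequency, at or after the injection. State how the date and severity of a worsening are recorded, so that this agrees with the maximal-severity rule in SAP 6.9.2 and Protocol 10.5.5.
3. Reconcile the end of SAE collection across Protocol 10.5.6.1, Protocol 10.5.6.2 and SAP 6.9. State that SAEs collected through 7 days after completion enter Tables 14.4.1.1, 14.4.1.4 and 14.4.1.5. Flag any that follow a treatment given after exit, which Protocol 4.1 permits.

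The cost is a few sentences in each document. No visits or assessments are added; the one new burden is the rule for entering a worsening in the eCRF.
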